**Table 1. SCHEDULE OF PROCEDURES**

	Screening	Treatment Period a								Follow-up b	ET	
		300 mg Gemcabene			600 mg Gemcabene		900 mg Gemcabene					
	up to Day -14	Day 1 c	Day 14	Day 28	Day 42	Day 56	Day 70	Day 84	Day 112			
	Visit S1	Visit T1	Visit T2	Visit T3	Visit T4	Visit T5	Visit T6	Visit T7				
Informed consent	X											
Inclusion/exclusion criteria	X											
Medical/surgical history and demographics	X											
Full physical examination d	X								X		X	
Symptom-directed physical examination		X	X	X	X	X	X		X e			
Vital signs f , height g , and weight	X	X	X	X	X	X	X	X			X	
Urinalysis h	X	X	X	X	X	X	X	X	X e		X	
Serum/urine pregnancy test i	X	X	X	X	X	X	X	X			X	
Safety chemistry panel, coagulation, and hematology j	X	X	X	X	X	X	X	X	X e		X	
TSH, HbA1c, and serology k	X											
Fasting lipid panel l	X	X	X	X	X	X	X	X			X	
Fasting apolipoproteins m		X		X		X		X			X	
hsCRP and fibrinogen		X		X		X		X			X	
CI		X							X		X	
Study drug administration		X	X	X	X	X	X	X				
Dispense study drug and instructions		X	X	X	X	X	X	X				
Compliance check		X	X	X	X	X	X	X			X	
Dietary instructions n	X	X	X	X	X	X	X	X				
PK sampling o		X	X	X	X	X	X	X			X	
12-lead ECG p	X q	X	X	X	X	X	X	X			X	
Adverse events	X q	X	X	X	X	X	X	X	X		X	
Concomitant medications	X	X	X	X	X	X	X	X	X		X	
Genetic testing		X										
Additional samples		X	X	X	X	X	X	X	X		X	

*Footnotes appear on the following page*

- a. Study assessments will be completed  $\pm 3$  days of given time point for all study visits from Day 1 through Day 70. Day 84 assessments can be performed up to 3 days prior to Day 84, but not after Day 84.
- b. The Follow-up Visit will be conducted as a telephone call 4 weeks ( $\pm 3$  days) after the last dose of study drug, unless the patient requires a site visit due to an abnormal result at Day 84 (or the ET Visit, if applicable) or an ongoing treatment-related adverse event.
- c. Procedures will be performed pre-dose. The Investigator will inquire with the patient at Day 1 to determine if there have been any changes in the patient's health affecting eligibility or requiring an update to their medical and surgical history.
- d. A full physical examination includes genitourinary examination per the Investigator's discretion and does not include a rectal examination. Assessment for xanthoma or arcus should also be part of the full physical examination. Any changes or improvements in xanthoma or arcus will be captured on the appropriate eCRF.
- e. Only for patients who had an abnormal result at Day 84 (or the ET Visit, if applicable) or an ongoing treatment-related adverse event.
- f. Vital signs include pulse rate, blood pressure, respiration rate, and temperature. Blood pressure should be obtained in the seated position, after the patient has rested comfortably for at least 5 minutes. Blood pressure at the Screening Visit should be obtained in both arms and the arm with the highest value should be used for ongoing monitoring throughout the rest of the study. If an automated assessment is performed, the same machine should be used for the patient throughout the study when possible. Care should be taken to ensure an appropriate cuff size is utilized.
- g. Height will be measured only at the Screening Visit.
- h. A urine microscopic examination will be performed when the dipstick result is abnormal (positive for blood, leukocyte esterase, or nitrites). Urine protein:creatinine ratio will be performed at the Screening Visit, Day 1, Day 28, Day 56, Day 84, the Follow-up Visit (only for patients who had an abnormal result at Day 84 [or the ET Visit, if applicable] or an ongoing treatment-related adverse event]), and the ET Visit, if applicable. Urinary NGAL will be measured at Day 1, Day 28, Day 84, the Follow-up Visit (only for patients who had an abnormal result at Day 84 [or the ET Visit, if applicable] or an ongoing treatment-related adverse event), and the ET Visit, if applicable.
- i. For women of child-bearing potential only, a serum pregnancy test will be conducted at the Screening Visit, Day 84, and the ET Visit, if applicable. A urine pregnancy test will be conducted at all other study visits, excluding the Follow-up Visit.
- j. Clinically significant abnormal creatinine results at Day 84 (or the ET Visit, if applicable) will also be followed-up 2 weeks ( $\pm 3$  days) after the last dose of study drug in addition to the 4 week ( $\pm 3$  days) Follow-up Visit. See Appendix B for a list of analytes and description of when repeat or reflexive testing will be required.
- k. Serology includes HBV, HCV, and HIV.
- l. Includes LDL-C, non-HDL-C, TC, TG, HDL-C, and VLDL-C. Fasting will be defined as no food or caloric beverage for at least 10 hours prior to sample collection. Patients will be permitted to have water.
- m. Includes ApoB, ApoA-I, ApoA-II, ApoC-II, ApoC-III, ApoE, and Lp(a). Fasting will be defined as no food or caloric beverage for at least 10 hours prior to sample collection. Patients will be permitted to have water.
- n. Patients will be counseled on a low-fat, low-cholesterol diet (NCEP ATP-III guidelines or equivalent).
- o. Pharmacokinetic samples will be collected pre-dose (must be  $24 \pm 2$  hours from the previous day's dose) and 0.5, 1, 2, 3, 5, and 12 hours post-dose on Day 28, Day 56, and Day 84 in collection tubes containing K2EDTA as the anticoagulant. For all other study visits where routine plasma drug monitoring will be performed (Day 1, Day 14, Day 42, Day 70, and the ET Visit, if applicable), samples will be collected pre-dose (must be  $24 \pm 2$  hours from the previous day's dose if a previous day's dose occurred). The window for PK samples obtained at time intervals  $<24$  hours will be  $\pm 10$  minutes.
- p. Electrocardiograms will be performed in triplicate and sent to a central reviewer. A 12-lead ECG will be performed at the Screening Visit and pre-dose on Day 1, Day 14, Day 42, Day 70, and the ET Visit, if applicable. Electrocardiograms will be performed pre-dose and 2 hours post-dose on Day 28, Day 56, and Day 84. Patients should be lying quietly in a fully supine position for at least 10 minutes prior to each 12-lead ECG.
- q. Serious adverse events that occur prior to the first dose of study drug (Day 1) should be reported as an update to medical history as well as be reported on the appropriate adverse event eCRF.

Apo = apolipoprotein; ECG = electrocardiogram; eCRF = electronic Case Report Form; ET = Early Termination; HbA1c = hemoglobin A1c; HBV = hepatitis B virus; HCV = hepatitis C virus; HDL-C = high-density lipoprotein cholesterol; HIV = human immunodeficiency virus; hsCRP = high-sensitivity C-reactive protein; K2EDTA = dipotassium ethylenediaminetetraacetic acid; LDL-C = low-density lipoprotein cholesterol; Lp(a) = lipoprotein(a); NCEP ATP-III = National Cholesterol Education

Program Adult Treatment Panel III; NGAL = neutrophil gelatinase-associated lipocalin; non-HDL-C = non-high-density lipoprotein; [REDACTED] C [REDACTED]  
[REDACTED] PK = pharmacokinetic; TC = total cholesterol; TG = triglyceride; TSH = thyroid-stimulating hormone; VLDL-C = very low-density lipoprotein cholesterol.

### 3 ANALYSIS VARIABLES

#### 3.1 Efficacy Variables

##### 3.1.1 Primary efficacy variable

The primary efficacy analysis is the percent change in LDL-C from baseline to Day 28, Day 56, and Day 84.

##### 3.1.2 Secondary efficacy variables

The secondary efficacy analyses are the following:

- The change in LDL-C from baseline to Day 28, Day 56, and Day 84;
- The change and percent change in lipid parameters (non-high-density lipoprotein cholesterol [non-HDL-C], total cholesterol [TC], triglycerides [TG], high-density lipoprotein cholesterol [HDL-C], and very low-density lipoprotein cholesterol [VLDL-C]) from baseline to Day 28, Day 56, and Day 84;
- The change and percent change in lipid parameters (LDL-C, non-HDL-C, TC, TG, HDL-C, and VLDL-C) from baseline to Day 28, Day 56, and Day 84 according to the receptor mutation status;
- The number (%) of patients achieving LDL-C reduction of  $\geq 15\%$ ,  $\geq 20\%$ ,  $\geq 25\%$ , and  $\geq 30\%$  at Day 28, Day 56, and Day 84;
- The number (%) of patients achieving an LDL-C value  $< 100$  mg/dL (2.59 mmol/L) at Day 28, Day 56, and Day 84, and at any time during the study;
- The change and percent change in apolipoprotein (Apo) B, ApoA-I, ApoA-II, ApoC-II, ApoC-III, ApoE, and lipoprotein(a) [Lp(a)] from baseline to Day 28, Day 56, and Day 84;
- The change and percent change in hsCRP from baseline to Day 28, Day 56, and Day 84; and
- The change and percent change in fibrinogen from baseline to Day 28, Day 56, and Day 84.

##### 3.1.3 Exploratory efficacy variables

CI

#### 3.2 Safety Variables

The safety variables include adverse events (AEs); safety laboratory parameters (chemistry, hematology, coagulation, and urinalysis) with particular attention to hepatic (e.g., alanine aminotransferase/aspartate aminotransferase, bilirubin, alkaline phosphatase), renal (e.g., blood urea nitrogen, serum creatinine, protein:creatinine ratio, urinalysis sediments, pH, electrolytes), and skeletal muscle (i.e., creatine kinase) toxicities; 12-lead electrocardiograms (ECGs); physical examinations (PEs); and vital signs.

### ***3.2.1 Adverse Events***

AEs will be assessed at all study visits and the Follow-up Visit. Adverse events that occur on or after the first dose of study drug (Day 1) will be considered treatment-emergent adverse events (TEAEs). Further details regarding AEs, such as the definition of an AE or serious adverse event (SAE), TEAEs, assessment of severity, assessment of causality, etc., are described in Section 9.1 and 9.2 of the protocol.

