5 STUDY TREATMENTS

5.1 Treatment Groups

During the 12-week Treatment Period, all patients will receive gemcabene 300 mg QD for 4 weeks, followed by 600 mg QD for 4 weeks, followed by 900 mg QD for 4 weeks.

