6.4 Follow-up Visit (Day 112)

The Follow-up Visit will be conducted as a telephone call 4 weeks (± 3 days) after the last dose of study drug, unless the patient requires a site visit due to an abnormal result at Day 84 (or the ET Visit, if applicable) or an ongoing treatment-related adverse event.

The following procedures will be performed at the Follow-up Visit (Day 112 ± 3 days):

- Perform symptom-directed physical examination (only for patients who had an abnormal result at Day 84 [or the ET Visit, if applicable] or an ongoing treatment-related adverse event);
- Collect urine sample for urinalysis including urine protein:creatinine ratio and NGAL (only for patients who had an abnormal result at Day 84 [or the ET Visit, if applicable] or an ongoing treatment-related adverse event);
- Obtain blood sample for safety chemistry panel, coagulation, and hematology (only for patients who had an abnormal result at Day 84 [or the ET Visit, if applicable] or an ongoing treatment-related adverse event); and
- Assess adverse events and update concomitant medications.

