9 SAFETY ASSESSMENTS

9.1 Adverse Events

An adverse event is defined as any untoward medical occurrence in a clinical investigation patient administered a pharmaceutical product, which does not necessarily have a causal relationship with this treatment. An adverse event can therefore be any unfavorable and/or unintended sign (including an abnormal laboratory finding), symptom, or disease temporally associated with the use of an investigational medicinal product, whether or not related to the investigational medicinal product. All adverse events, including observed or volunteered problems, complaints, or symptoms, are to be recorded on the appropriate eCRF.

Adverse events, which include abnormal and clinically significant clinical laboratory test variables, will be monitored and documented from the time of first dose of study drug (Day 1) until study participation is complete (the Follow-up Visit). Patients should be instructed to report any adverse event that they experience to the Investigator. Beginning with the signing of the informed consent until the time of the first dose of study drug (Day 1), investigators should make updates to medical history and record any pre-existing medical condition or signs or symptoms that changes in severity, frequency, or seriousness in the medical history. Serious adverse events that occur prior to the first dose of study drug (Day 1) should be reported as an update to medical history as well as be reported on the appropriate adverse event eCRF. Beginning with the first dose of study drug (Day 1), investigators should make an assessment for adverse events at each visit and record all adverse events, non-serious and serious, on the appropriate adverse event eCRF.

Wherever possible, a specific disease or syndrome rather than individual associated signs and symptoms should be identified by the Investigator and recorded on the eCRF. However, if an observed or reported sign or symptom is not considered a component of a specific disease or syndrome by the Investigator, it should be recorded as a separate adverse event on the eCRF. Additionally, the condition that led to a medical or surgical procedure (e.g., surgery, endoscopy, tooth extraction, or transfusion) should be recorded as an adverse event, not the procedure. Concomitant procedures should be recorded as such on the appropriate eCRF.

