## **8.2 Adverse Events**

AEs will be coded using the most recent version of the Medical Dictionary for Regulatory Activities (MedDRA) and summarized by treatment group, system organ class, and preferred term.

A summary overview of TEAEs will be provided which presents the number and percentage of patients in each treatment group satisfying each of the following categories:

- All TEAEs,
- Drug-related TEAEs,
- Maximum severity of TEAEs,
- Maximum severity of drug-related TEAEs,
- All treatment-emergent SAEs,
- Drug-related treatment-emergent SAEs,
- Death due to TEAEs,
- TEAEs leading to study drug discontinuation, and
- Drug-related TEAEs leading to study drug discontinuation.

The numbers and percentages of patients with TEAEs will be summarized by MedDRA preferred term within system organ class, by treatment group and overall. For the summaries by treatment group, multiple AEs with the same MedDRA preferred term within system organ class from the same patient within a given treatment will only be counted once. For overall summaries, multiple AEs with the same MedDRA preferred term within system organ class from the same patient will only be counted once. The AE onset date will determine the treatment group classification for the AE.

All TEAEs related to study drug, SAEs, and AEs leading to study drug discontinuation will be summarized in the same manner. Summaries will also be provided for the numbers and percentages of patients by system organ class, preferred term, and maximum severity, for TEAEs and drug-related TEAEs.

All AEs will be included in by-patient listings containing additional information of interest such as onset and resolution times, maximum severity, causal relationship to study medication, and action taken. Specific by-patient listings of SAEs and TEAEs leading to study discontinuation will be provided.

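### The plan gives TEAEs no end date and no post-treatment column, so a completer's off-drug adverse events can only fall under 900 mg, which would bias that column's percentage upward

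*SAP*

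**What the plan says.** **Start, but no end.** SAP 3.2.1 defines the window: "Adverse events that occur on or after the first dose of study drug (Day 1) will be considered treatment-emergent adverse events (TEAEs". It sends the reader to Protocol 9.1 and 9.2 for further detail, but neither section defines a TEAE or closes the window.

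**Collection runs past the last dose.** Under Protocol 9.1, AEs "will be monitored and documented from the time of first dose of study drug (Day 1) until study participation is complete (the Follow-up Visit". SAP 3.2.1 agrees: "AEs will be assessed at all study visits and the Follow-up Visit". Protocol 6.4 places that visit 4 weeks (±3 days) after the last dose, by telephone unless a site visit is needed.

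**Tabulation.** SAP 8.2 presents numbers and percentages of patients with TEAEs, which "will be summarized by MedDRA preferred term within system organ class, by treatment group and overall". It allocates them as follows: "The AE onset date will determine the treatment group classification for the AE". It names no post-treatment column, no cutoff relative to the last dose and no time-adjusted rate.

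**Dose order.** Protocol 5.1 fixes the sequence at 300, 600, then 900 mg, 4 weeks each. SAP 2.2 plans no break between doses.

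**Exposure.** SAP 8.1 counts days within a dose level from first to last dose, so exposure excludes follow-up.

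**The concern.** The 300 mg and 600 mg windows close when the next dose starts. The last dose has no successor. If its window stays open to the Follow-up Visit, the columns compare percentages of patients with at least one event over unequal observation times, and half of the longest is off drug.

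Safety and tolerability are part of the primary objective (SAP 2.1.1), and safety data feed the choice of a Phase 3 dose (SAP 2.1.2). SAP 8 rests the safety analysis mainly on how often new or worsening events occur, which is the quantity affected. The artefact runs the same way as a true dose effect, and in a single-arm, fixed-order study the by-dose table cannot separate the two. A reader would also see about 28 days of 900 mg exposure beside AEs gathered over about 56 days.

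Interim analysis #2 (SAP 10) adds a further imbalance. Its cutoff is the last subject's Week 12 visit, so earlier patients could contribute follow-up time and the last could not.

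**Working it through.** **1. Check the calendar.** Screening 14 days + treatment 84 days + follow-up 28 days = 126 days = 18 weeks. This matches the stated maximum study duration.

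**2. AE windows for a completer.** The ranges use the visit windows in Protocol 6.3 and 6.4: Day 28 ±3, Day 56 ±3, Day 84 −3/+0, and follow-up 25 to 31 days after the last dose.

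| Column | Nominal days | Length | Range |
|---|---|---|---|
| 300 mg | 1–28 | 28 | 25–31 |
| 600 mg | 29–56 | 28 | 22–34 |
| 900 mg, on drug | 57–84 | 28 | 81−59 = 22 to 84−53 = 31 |
| 900 mg plus follow-up | 57–112 | 56 | 22+25 = 47 to 31+31 = 62 |

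The nominal ratio is 56/28 = 2.

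**3. Effect on the percentage.** Two quantities must be assumed, because the documents give neither:
- p, the 4-week risk of at least one AE, taken to be the same at every dose (no dose effect);
- f, the off-drug AE hazard, or chance of detection, relative to on drug.

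With a constant hazard within each phase, the 300 mg and 600 mg columns each show p. The 900 mg column shows 1 − (1−p)^(1+f).

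| p | f = 0 | f = 0.25 | f = 0.5 | f = 1 |
|---|---|---|---|---|
| 10% | 10% | 12.3% | 14.6% | 19.0% |
| 20% | 20% | 24.3% | 28.4% | 36.0% |
| 30% | 30% | 36.0% | 41.4% | 51.0% |
| 50% | 50% | 58.0% | 64.6% | 75.0% |

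Example: p = 0.20 and f = 0.5 gives 1 − 0.8^1.5 = 0.284, a ratio of 1.42.

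In 8 patients with p = 30%, the lower-dose columns each expect 8 × 0.30 = 2.4 patients. The 900 mg column expects 2.9, 3.3 or 4.1 for f = 0.25, 0.5 or 1.

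**4. Sign.** For any f above zero, (1−p)^(1+f) is less than 1−p, so the expected bias is upward. It vanishes only at f = 0, when no new AEs are recorded off drug.

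**5. After the change.** With off-drug onsets in their own column, the nominal dose windows are 28, 28 and 28 days. Under no dose effect, all three columns then expect p.

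**The case against.** **The allocation to 900 mg is inferred.** On Days 85–112 no dose is being taken, so an onset date there points to no dose group. Such AEs could be counted under overall alone, which would fit the exposure definition in SAP 8.1. The table shells are stand-alone documents (SAP 5.4) and may already settle it. This stands as a limit on certainty. But counting these AEs only under overall also needs a rule that the SAP lacks, and the allocation should be written down before database lock on either reading.

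**Off-drug detection is probably lower.** Follow-up is a telephone call by default, with examination and laboratory tests only for certain patients (Protocol 6.4). The 900 mg period has two site visits with laboratory tests and ECGs (Protocol 6.3.6 and 6.3.7). This stands, and is why f is varied. At p = 30%, the two lower values of f give an excess of less than one patient in 8.

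**Early off-drug AEs may be real effects of the last dose.** Protocol 1.3 reports that creatinine rises resolved within about 2 weeks of stopping, so drug effects can persist after the last dose. This stands in part. However, any lag added after the last dose lengthens only the final column, because the lower doses have no washout.

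**The effect on decisions is limited.** About 8 patients are planned and the AE summaries are descriptive. Listings give onset times and causality, the fixed sequence already confounds dose with time, and the dose choice also draws on efficacy, PK and other studies (Protocol 3.1). All true, and the fix does not remove that confounding. It does remove an avoidable bias added on top of it. The drug-related TEAE tables follow the same classification, so they do not avoid the problem.

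**Conclusion.** The point holds as a gap whose most natural reading produces a bias. The written rules leave a completer's post-treatment AEs no dose column except 900 mg. That column would cover nominally 56 days (47–62 with visit windows) against nominally 28 for each lower dose. The percentage of patients with a TEAE at 900 mg would be biased upward relative to the lower doses.

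Two stronger readings are tempting, and the documents support neither:
- *The SAP assigns follow-up AEs to 900 mg.* It does not say so. This follows only from an open-ended definition, allocation by onset date and the absence of another dose column.
- *The 900 mg incidence would be about double.* Observation time doubles, but the percentage need not. Even with equal hazard on and off drug, the ratio is 1.9 at 10% risk, 1.8 at 20%, 1.7 at 30% and 1.5 at 50%. With f at one-half or one-quarter, it is 1.42 or 1.22 at 20% risk.

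The size is unknown. The illustrations rest on an assumed 4-week risk, no dose effect, and a constant hazard within the on-drug and off-drug phases. The LDL-C analysis is unaffected. This is a cheap improvement to the by-dose safety tables.

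**What to change.** In SAP 8.2, state that:
- each by-dose column counts AEs with onset from the first to the last dosing day at that level;
- AEs with onset after the last dose of study drug go in a separate post-treatment follow-up column;
- those AEs also count in the overall column.

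Apply the same rule to patients who stop early on 300 mg or 600 mg, whose off-drug AEs would otherwise fall to the last dose taken, and to the AE summary in interim analysis #2.

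The cost is a short addition to the SAP and one table column. The dosing dates are already needed for exposure in SAP 8.1. The downside is that a delayed effect of the last dose appears in the follow-up column instead of the dose column. It stays visible there, in overall and in the by-patient listings.

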### ***3.2.2 Safety Laboratory Evaluations***

Standard clinical laboratory evaluations for safety chemistry, coagulation, hematology, and urinalysis will be conducted at all study visits and the Follow-up Visit (only for patients who had an abnormal result at Day 84 [or the ET Visit, if applicable] or an ongoing treatment-related adverse event). Clinically significant abnormal creatinine results at Day 84 (or the ET Visit, if applicable) will also be followed-up 2 weeks ( $\pm 3$  days) after the last dose of study drug in addition to the 4 week ( $\pm 3$  days) Follow-up Visit.

